9.3 Cryotherapy

As per Seattle Cancer Care Alliance protocol, patients will hold ice chips in the mouth from up to 30 min prior through the end of the oxaliplatin infusion. The use and duration of ice chip exposure will be documented. Additionally, the use of ice packs on hands and/or feet (which is allowed, but not part of current standard-of-care cryotherapy) will also be documented. Duration of each will be recorded as 0, 1-30, 31-60, 61-90, 91-120, or >120 minutes. Patients will be given the Cryotherapy Questionnaire (Appendix O) on the day of infusion or contacted by study staff within 5 days of completion of their chemotherapy infusion and patient self-recall will be used to determine the method and duration of their cryotherapy (Appendices O and P). The Questionnaire may also be sent via email to be complete in the study portal.

9.4 Waitlist Control

To increase participant willingness to be randomized and to increase trial retention, participants randomized to the control arm will receive coupons for six acupuncture treatments at SCCA South Lake Union clinic to be used any time after completion of the individual's duration (approximately 12 weeks) on the study (Appendices M and N). At the time of these visits, AEs and limited exam findings may be collection, which will be entered into the database as well. These visits will ideally be during or coordinated with standard-of-care visits. However, if patients have completed treatment, they may attend acupuncture-only visits.

9.5 Concomitant Medication and Supportive Care Guidelines

The use of duloxetine and selective serotonin-norepinephrine reuptake inhibitors (SNRIs) are not permitted while on this study. Selective serotonin reuptake inhibitors (SSRIs) are permitted if prescribed for an indication other than the treatment of neuropathy (such as depression or anxiety).

Additional medications prescribed for the treatment of chemotherapy-induced peripheral neuropathy are not permitted. This includes gabapentin, alpha lipoic acid, B complex vitamin (or B1, B6, B12). These agents are permitted if prescribed for another indication.

Standard-of-care supportive care is recommended for the treatment of fatigue, pain, nausea, oral dysesthesia, and anxiety, and any other symptoms related to cancer or chemotherapy treatment.

9.6 Duration of Therapy

The intervention will be delivered over 3 months, concurrent with chemotherapy.

9.7 Duration of Follow-Up

Patients will not be followed after the intervention and end-of-treatment questionnaires are complete, with the exception of collection of data during waitlist control acupuncture visits if these are pursued.

9.8 Dosing Delays/Dose Modifications

Dose modifications, hold, and other alterations to planned chemotherapy will be at the discretion of the treating physician. Acupuncture treatments will be moved accordingly to co-occur with the chemotherapy treatments. If a patient discontinues use of oxaliplatin, he/she may continue to receive acupuncture either weekly or as protocolized (twice weekly every other week) until the completion of 3 months duration of acupuncture treatment.

9.9 End of Treatment (EOT) Visit Schedule and Procedures

The EOT visits for all subjects who discontinue from the study should ideally occur 14 days after day 1 of the prior cycle of chemotherapy (which would be 11 days from the last acupuncture treatment). The EOT visit is permitted in the range of 7-30 days after the last use of (Arm A) acupuncture treatment or (Arm B) cryotherapy use but must occur prior to beginning another treatment or receiving another dose of chemotherapy. Procedures to be performed during the EOT Visit include:

- Physical Exam
- Administration of the final QOL measures
- Vital Signs
- Performance Status
- AE Assessment
- Concomitant Medication

As per 6.7. patients who are on the waitlist control arm and choose to use their acupuncture coupons will have the optional EOT visit for uniform data collection, but will also have limited data collected at the time of each acupuncture session to note any toxicities or major symptoms at the time of those visit.

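### Section 9.9 counts the EOT range from a different event in each arm, so after an early oxaliplatin stop the final CIPN-20 can be timed differently by arm and away from week 12

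*Combined protocol and SAP*

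**What the plan says.** **Where the final score is taken.** Section 9.9 lists "Administration of the final QOL measures" among the EOT procedures. In the study calendar (Appendix B) the last PRO column is End of Tx. There is no separate week-12 column, and footnote 7 refers the timing back to 9.9.

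**Timing rules in 9.9.** The visit "should ideally occur 14 days after day 1 of the prior cycle of chemotherapy (which would be 11 days from the last acupuncture treatment"). It is "permitted in the range of 7-30 days after the last use of (Arm A) acupuncture treatment or (Arm B) cryotherapy use". It also "must occur prior to beginning another treatment or receiving another dose of chemotherapy".

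**What moves each anchor.** In Arm B, section 9.3 ties cryotherapy to the infusion: "patients will hold ice chips in the mouth from up to 30 min prior through the end of the oxaliplatin infusion". Last use therefore cannot be later than the last oxaliplatin dose. In Arm A, section 9.8 (repeated in 11.0) says: "If a patient discontinues use of oxaliplatin, he/she may continue to receive acupuncture either weekly or as protocolized", up to 3 months of acupuncture. Section 11.0 also lists a change to a regimen without oxaliplatin among the reasons for which study treatment must stop.

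**The common time point.** Section 10.2 sets the CIPN-20 at baseline, 6 weeks and 12 weeks in both arms. Section 16.5 compares the 3-month score by linear regression adjusted for baseline. Section 9.7 says: "Patients will not be followed after the intervention and end-of-treatment questionnaires are complete", with an exception for data collected at waitlist acupuncture visits.

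**The concern.** The two anchors behave differently once oxaliplatin stops. Arm B's is fixed at or before the last dose, while Arm A's can run on for weeks. The visit rule itself can then place the primary outcome at a different time since last oxaliplatin in each arm, and in Arm B well before the 3 months that 16.5 analyses.

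The CIPN-20 asks about the past week (Appendix D), so each score describes the 7 days before it is completed. The background in 5.1 cites an adjuvant FOLFOX trial with CIPN in more than 90% of patients during treatment and 15% with symptoms four years later. The level is therefore not constant over time, although 5.1 gives nothing on the scale of weeks. The regression adjusts for baseline only, and a larger sample would not remove a timing difference that the visit rule creates.

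**Working it through.** **Inputs.** Biweekly cycles x6 with acupuncture on days 1 and 3 (9.2); EOT range 7-30 days (9.9); 12-week assessment (10.2). Take C1D1 as day 1, with no delays. Day 1 of cycle k is d = 14(k-1)+1, so C6D1 = 71 and C6D3 = 73. Twelve weeks after C1D1 is 1+84 = day 85.

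**The plan's own target, on schedule.** 71+14 = day 85, which agrees with 12 weeks. The distance from the last session is 85-73 = 12 days, where 9.9 gives 11.

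**On-schedule ranges.** Arm A: 73+7 to 73+30 = days 80-103. Arm B: 71+7 to 71+30 = days 78-101. The anchors differ by 2 days and both ranges contain day 85.

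**Early stop, Arm A acupuncture continued to day 73, no new treatment first.** Arm A stays at 80-103. Arm B is d+7 to d+30, with ice used at the last infusion.

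| Last oxaliplatin cycle (d) | Arm B range | Days from Arm B close to Arm A open | Arm B closes before day 85 by | Days since last oxaliplatin, Arm B / Arm A |
|---|---|---|---|---|
| 1 (1) | 8-31 | 49 | 54 | 7-30 / 79-102 |
| 2 (15) | 22-45 | 35 | 40 | 7-30 / 65-88 |
| 3 (29) | 36-59 | 21 | 26 | 7-30 / 51-74 |
| 4 (43) | 50-73 | 7 | 12 | 7-30 / 37-60 |
| 5 (57) | 64-87 | overlap, days 80-87 | contains day 85 | 7-30 / 23-46 |

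These are outer limits. If biweekly chemotherapy continues without oxaliplatin, the next-dose clause caps Arm B at d+14. At cycle 5 that gives 64 to 57+14 = 71, so the overlap disappears and day 85 is missed.

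**Acupuncture stops with oxaliplatin.** The last session is d+2, so Arm A is d+9 to d+32: 10-33, 24-47, 38-61, 52-75 and 66-89 for cycles 1-5. The offset from Arm B is 2 days throughout. After a stop in cycles 1-4, Arm A closes by day 75 and Arm B by day 73, both before day 85.

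**Weekly continuation (assumed last session).** A last session on day 78 gives Arm A 85-108. A last session on day 85 gives 92-115, which itself misses day 85.

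**Does the 9.9 target settle it?** If all chemotherapy ends, the target is d+14 = 15, 29, 43, 57 or 71. That lies inside Arm B's range but 65, 51, 37, 23 or 9 days before Arm A's opens at day 80. If chemotherapy without oxaliplatin runs to cycle 6, the target is day 85. After a stop in cycles 1-4 that is 84, 70, 56 or 42 days after Arm B's last cryotherapy, beyond the 30-day limit.

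**The case against.** The strongest reply is that a common rule already exists. Section 10.2 requires the CIPN-20 at 12 weeks without exception for arm or oxaliplatin status, 16.5 analyses 3 months, and 9.9 opens with patients who discontinue from the study, which stopping oxaliplatin is not stated to be. On that view the trouble is loose drafting rather than an intended arm-specific endpoint. This stands in part. But the calendar sends the timing of every final PRO to 9.9, and no passage says that 10.2 overrides it.

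The disjoint case also needs several conditions. Continuation of acupuncture is optional. If the 11.0 mandatory-stop item governs, acupuncture stops too and the offset is 2 days. A new treatment begun before day 80 removes the Arm A range altogether. All of this stands and limits the scope of the point.

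A reader might infer that an Arm B patient seen within the range can have no later CIPN-20. The documents do not support that flatly. Section 9.7 excepts waitlist visits, and 9.9 mentions an optional EOT visit for patients who use their coupons. The calendar's waitlist column shows no PROs, so the matter is unclear rather than closed.

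A reader might also infer that the trial result is biased towards one arm. The documents give no early-stop rate and no course of CIPN-20 over weeks, so neither size nor direction follows.

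**Conclusion.** The point holds for early oxaliplatin stoppers only, and it should be fixed. For patients on schedule the difference is 2 days and unimportant. After a last dose in cycles 1-4, with Arm A acupuncture continued to day 73 and no new treatment first, the permitted ranges share no day and lie 7 to 49 days apart. If acupuncture stops with oxaliplatin, the arms are aligned to within 2 days, but both ranges miss the 12 weeks of 10.2.

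How often the disjoint case arises depends on the early-stop rate, which is not given, and on the conflict between the 11.0 stop item and the 9.8/11.0 sentence allowing continuation. Those passages must be reconciled. The figures assume 14-day cycles without delay and ice use at the last infusion. Confidence is medium, because the rule is explicit but its practical reach is unknown.

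Three details are minor and separate: skipped ice moves or removes the Arm B anchor; read literally, an Arm A patient whose last session is C4D3 has a range (45+7 to 45+30 = days 52-75) that closes before week 12; and 9.9 gives 11 days where its schedule gives 12.

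**What to change.** In 9.9 and Appendix B footnote 7, state that the final CIPN-20 and other PROs are collected in both arms in one window around 12 weeks from C1D1 (day 85), moved by recorded chemotherapy delays, whatever the date of last acupuncture or cryotherapy.

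- **Width.** Use the same width in both arms, with an opening that keeps at least 7 days after the last on-schedule session (73+7 = day 80). Days 80-92 is one example; the width is the sponsor's choice. Completion comes before any chemotherapy that day and, for patients still on oxaliplatin, before the next dose. For a patient dosed on day 85 the example window is therefore days 80-85.
- **Early stoppers.** Apply the same window, with PROs collected by phone, on paper or electronically, as 10.2 already allows at C4D8. For a stop in cycle 1, 2, 3, 4 or 5, days 80-92 are 79-91, 65-77, 51-63, 37-49 or 23-35 days after last oxaliplatin in both arms.
- **Alignment.** Adjust 9.7 and the 9.9 clause on visits preceding another treatment so that the week-12 questionnaire is still collected. Reconcile the 11.0 stop item with the continuation sentence.
- **Analysis.** Record days since last oxaliplatin. Any analysis using it is exploratory and should be labelled post-randomisation.

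The cost is wording in a few places and no extra patients. Some early stoppers will be assessed later, possibly on a new regimen, and some in-person Neuropen and tuning fork tests will be missing. If stopping itself differs by arm, time since last oxaliplatin can still differ, but no longer because of the visit rule.

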10.0 SUBJECT EVALUATION

10.1 On-Study Clinical Evaluations

Clinical evaluations take place according to the Study Calendar (Appendix B). The window between these visits should be as close to the scheduled time as possible, though delays in chemotherapy treatment as recommended by the treating physician are permitted and do not require cessation of protocol therapy.

- **Vitals**
 - Include blood pressure, pulse, temperature
- **Physical Exam**
- **Performance Status**
 - As per the ECOG performance scale (see Appendix A)
- **Labs (day 1 of each cycle, or up to 3 days prior):**
 - Hematology: CBC with absolute neutrophil count and platelets
- **Acupressure Diary (see Appendix J)**
 - Assessment of self-administered acupressure will be reviewed on day 1 of cycle 2 and each subsequent cycle. Patients who complete <50% of the prescribed acupressure regimen will be re-educated at cycle 2 on appropriate execution of the recommended acupressure regimen.
- **Clinical AE attribution**
 - CTCAE version 5.0

10.2 Quality of Life Assessments

These will be administered at baseline, 6 weeks, and 12 weeks. If a patient is receiving chemotherapy on the day of the assessments, the assessments must be completed before the chemotherapy treatment is administered.

At each time point the EORTC QLQ CIPN-20 (see Appendix D) will be used to assess neuropathy and targeted questions from the NCI-PRO CTCAE (Appendix E) for the assessment of fatigue, nausea, and anxiety. The Brief Pain Inventory (Appendix F) will be used to assess pain. An oral symptoms questionnaire (Appendix G) will be used to assess oral dysesthesia.

On cycle 4 day 8 (± 2 days), a mid-cycle assessment will be done for the EORTC-QLQ CIPN-20, NCI-PRO CTCAE, and BPI. This may be administered by phone, on paper and returned at next clinic appointment, or electronically.

10.3 Neuropathic Assessments

These will be administered at baseline, 6 weeks, and 12 weeks. If a patient is receiving chemotherapy on the day of the assessments, the assessments must be completed before the chemotherapy treatment is administered.

10.3.1 Neuropen

The Neuropen is used to assess sensation with a 10g monofilament on one end and 40g Neurotip on the other end. For each patient evaluation, a 10-point examination of the dominant foot will be performed. After 100 such examinations, the monofilament needs to be replaced. The Neurotip is single use and must be replaced after each patient examination. A study-specific Neuropen will be used for all patient assessments by a trained clinician or research staff member.

Neuropen training will consist first of reviewing the user manual and instructional video for the Neuropen, which will follow standard protocols as described for the prior neuropathy trial SWOG 1714 (<https://www.swog.org/required-s1714-training>). Secondly, the staff member will need to be observed by [name], or another trained member of the study team.

Touch and Pressure Perception: Touch and pressure sensation is assessed using the 10-g monofilament in the Neuropen on the subject's dominant foot. The dominant foot can be identified by asking the subject with which foot they would kick a ball. The clinician will follow the subsequent steps using the subject's dominant foot:

1. Ask the subject to remove sock and/or shoe on the dominant foot and lay flat or sit up on an examination table.
2. Fully extend the monofilament by sliding the button to the end of the device until a click is heard.
3. Wipe the end of the monofilament with an alcohol wipe or antiseptic solution.

4. The 10 sites in the below figure (Figure 7.1) are to be tested at random on the dominant foot. Press the monofilament at a 90-degree angle to the skin surface and increase the pressure until it bows. The subject should not be able to see which site is being tested.
5. Hold in position for 1-2 seconds.
6. For each of the 10 sites tested, ask the subject if he/she can detect pressure applied from monofilament and name the location of sensation. Subjects may use the unmarked picture of the feet (similar to what is shown in Appendix H) to point to the location of sensation if they are unable to adequately name the location. Record subject response for each site tested.

Protective Pain and Sharpness Sensation: This is a calibrated and sterile pain/sharpness test on the subject's dominant foot. The spring mechanism is calibrated to exert a force of 40 grams to help identify subjects with a loss of pain sensation. The dominant foot can be identified by asking the subject with which foot they would kick a ball. The clinician will follow the subsequent steps using the subject's dominant foot:

1. Ask the subject to remove sock and/or shoe on the dominant foot and lay flat or sit up on an examination table.
2. Take an unused Neurotip and hold by the cap. Do not use if Neurotip cap has previously been removed.
3. Press Neurotip firmly down into the Neurotip carrier of the Neuropen as far as it will go and clicks into position. The Neurotip is correctly positioned when only one chevron can be seen on the Neurotip.
4. To expose the sterile semi-sharp tip, place thumb gently over the Neurotip pressure gauge and remove Neurotip cap by twisting and pulling outwards.
5. The 10 sites in the below figure (Figure 7.1) are to be tested at random. Press the Neurotip against the skin surface at a 90-degree angle. The subject should not be able to see which site is being tested.
6. Hold in position for 1-2 seconds before removing, taking care to depress within the 40-gram marked white area.
7. For each of the sites tested, ask the subject if they detect a sharp sensation and name the location of sharp sensation. Subjects may use the unmarked picture of the feet (similar to what is shown in Appendix H) to point to the location of sensation if they are unable to adequately name the location. Record subject response for each site tested.
8. Remove and discard the used Neurotip in an appropriate sharps container after completing the 10 site examinations.

10.3.2 Tuning fork

A study-specific 128-Hz tuning fork will be used to assess sensation by a trained clinician or research staff member. As above, this will consist first of reviewing the user manual and instructional video for the tuning fork, which will follow standard protocols as described for the prior neuropathy trial SWOG 1714 (<https://www.swog.org/required-s1714-training>). Secondly, the staff member will need to be observed by [name], or another trained member of the study team.

Dominant Lower Extremity Vibration Sensation Testing

1. The tuning fork should be firmly tapped on the palm of the hand of the clinician to initiate vibration.
2. The vibrating tuning fork is first placed on the interphalangeal joint of the great toe of the dominant foot (Appendix I [A]). The dominant foot can be identified by asking the subject with which foot they would kick a ball. A timer is started once the vibrating tuning fork is placed on the interphalangeal joint of the great toe of the dominant foot.
3. The patient is instructed to report when vibration is no longer detected. The time at which the vibration is no longer detected should be noted.
4. If the patient feels the vibration for 15 seconds or longer, this is defined as normal and should be recorded as such. If vibration sensation is normal at the great toe, additional assessments of the lower extremity are not needed.
5. If vibration sensation in the great toe of the dominant foot is less than 15 seconds, this is defined as absent or decreased vibration sensation and should be recorded as such. If vibration sensation is absent or decreased in the interphalangeal joint of the great toe of the dominant foot, the clinician then conducts the testing at all additional sites listed below on the dominant side. For each site tested, the tuning fork should be firmly tapped on the palm of the hand of the clinician to initiate vibration and the vibrating tuning fork is placed on the site. Once the vibrating tuning fork is placed on the testing site, a timer is started to measure the time at which the vibration is no longer detected. This time should be noted for each site.
 - a. The middorsal foot (Appendix I [B]): If the patient feels the vibration for 15 seconds or longer, this is defined as normal. If the patient feels the vibration less than 15 seconds, this is defined as absent or decreased vibration sensation.
 - b. The medial malleolus (ankle) (Appendix I [C]): If the patient feels the vibration for 15 seconds or longer, this is defined as normal. If the patient feels the vibration less than 15 seconds, this is defined as abnormal.
 - c. The midfibular region of the dominant lower extremity (Appendix I [D]): If the patient feels the vibration for 15 seconds or longer, this is defined as normal. If the patient feels the vibration less than 15 seconds, this is defined as absent or decreased vibration sensation.

d. The patellar region of the dominant lower extremity (Appendix I [E]): If the patient feels the vibration for 10 seconds or longer, this is defined as normal. If the patient feels the vibration less than 10 seconds, this is defined as absent or decreased vibration sensation.

Dominant upper extremity vibration sensation testing

1. The clinician will conduct the testing at all three sites below on the dominant upper extremity. The dominant upper extremity can be identified by asking the subject with which hand they write.
2. For each site tested, the tuning fork should be firmly tapped on the palm of the hand of the clinician to initiate vibration and the vibrating tuning fork is placed on the site. Once the vibrating tuning fork is placed on the testing site, a timer is started to measure the time at which the vibration is no longer detected. This time should be noted for each site. The three sites to be tested on the dominant upper extremity vibrating tuning fork are:
 - a. The distal interphalangeal joint of the index finger (Appendix I [F]): If the patient feels the vibration for 25 seconds or longer, this is defined as normal. If the patient feels the vibration less than 25 seconds, this is defined as absent or decreased vibration sensation. Regardless of sensation at site (a), all three upper extremity sites will be tested.
 - b. The ulnar styloid (wrist) (Appendix I [G]): If the patient feels the vibration for 15 seconds or longer, this is defined as normal. If the patient feels the vibration less than 15 seconds, this is defined as absent or decreased vibration sensation.
 - c. The lateral epicondyle (elbow) (Appendix I [H]): If the patient feels the vibration for 15 seconds or longer, this is defined as normal. If the patient feels the vibration less than 15 seconds, this is defined as absent or decreased vibration sensation.

